perform “repeat” visits on two healthy volunteers. This will provide essential quantitative information on some novel mitochondrial parameters that are measured in the MiSBIE study (cell bioenergetics, cell-free mitochondrial DNA, metabolic markers), including how they may vary within a person over time, relative to between- person differences. These difficult to obtain data can be used to quantify intra- individual variation over months-to-years and provide an empirical basis to evaluate the magnitude of differences among the primary study outcomes between the MiSBIE study groups.

Description of Subject Population

Sample #1

Sample subject population:

Subject Population	Number of completers required to accomplish study aims	Projected number of subjects who will be enrolled to obtain required number of completers	Age range of subject population
Individuals with the m.3243A>G mitochondrial DNA mutation	30	33 (accounting for 10% attrition or unusable data)	18 to 60

Description of subject population:

We will investigate individuals carrying the m.3243A>G tRNA^{Leu(UUR)} mutation which is the most frequent mtDNA point mutation, and presents in the most severe case as MELAS (Mitochondrial Encephalopathy, Lactic Acidosis, and Stroke-like episodes) (50, 51) as well as non-MELAS carrier relatives. From this cohort and the existing patient registry, individuals who have previously had genetic diagnostic testing confirming the presence of the m.3243A>G will be identified and invited to participate in the study. Maternally related individuals with a first-degree relative who is a known carrier of the mutation are considered “obligate carriers” and will also be included.

Individuals without a confirmed genetic test who are otherwise eligible and who have family members with 3243A>G mitochondrial DNA mutation and/or suspect they have the mutation will be invited to provide a buccal or urine sample to test for mitochondrial mutations. The genetic counselor or physician will review the specific consent form for genetic testing

Protocol Summary Form

[Genetic Testing Consent Form MiSBIE], and sample collection instructions remotely with these participants or at the Columbia University Irving Medical Center research site.

Sample #2

Sample subject population:

Subject Population	Number of completers required to accomplish study aims	Projected number of subjects who will be enrolled to obtain required number of completers	Age range of subject population

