Individuals with single large-scale mitochondrial DNA deletions	30	33 (accounting for 10% attrition or unusable data)	18 to 60

Description of subject population:

We will investigate individuals carrying a single large-scale mtDNA deletions that causes CPEO (chronic progressive ophthalmoplegia) and Kearns-Sayre syndrome (KSS) (52). [name] follows >20 patients with CPEO/KSS, and leads a national consortium (NAMDC – North American mitochondrial disease consortium) where >70 patients with CPEO/KSS have consented to be contacted for research. From this group, patients who have previously had diagnostic testing confirming the presence of mtDNA single deletion will be identified and invited to participate in the study.

Individuals without a confirmed genetic test who are otherwise eligible and who have family members with single large-scale mitochondrial DNA deletions and/or suspect they have the deletion will be invited to provide a buccal or urine sample to test for mitochondrial mutations. The genetic counselor or physician will review the specific consent form for genetic testing [Genetic Testing Consent Form MiSBIE], and sample collection instructions remotely with these participants or at the Columbia University Irving Medical Center research site.

Sample #3

Sample subject population:

Protocol Summary Form

Subject Population	Number of completers required to accomplish study aims	Projected number of subjects who will be enrolled to obtain required number of completers	Age range of subject population
Controls	100	118 (accounting for 10% attrition or unusable data n=10 and pilot testing n=8)	18 to 60

Description of subject population:

We will study healthy individuals without a diagnosis of mitochondrial disease recruited from the community. These participants will be age-, sex- and physical activity level- matched to participants from Groups 1 and 2.

Sample #4

Sample subject population:

Subject Population	Number of completers required to accomplish study aims	Projected number of subjects who will be enrolled to obtain required number of completers	Age range of subject population
Individuals with the m.3243A>G mitochondrial DNA mutation with MELAS symptoms. This is the same diagnostic group as Group 1, with the exception that patients who have experienced stroke-like episodes or seizures will not be excluded	30	33 (accounting for 10% attrition or unusable data)	18 to 60

New York State
Psychiatric Institute
Institutional Review Board
 PRISM 2022

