5. Carries the m.3243A>G point mutation and has had at least one stroke-like episode, seizure, or both.	Patient clinical records, or family history involving them as "obligate carrier" of the mtDNA defect
6. English Speaking	Self-report Phone screen or clinical evaluation
7. Confirmatory genetic test or willing to undergo genetic testing if one is not available.	Medical Records Genetic Test
Exclusion:	
1. Patients with cognitive deficit incapable of providing informed consent will not be included	TICS scores \geq 30, administered via phone screen or clinical evaluation
2. Neoplastic disease	Patient clinical records, and self-report
3. Symptoms of flu or other seasonal infection four weeks preceding hospital visit, as this would influence immune system parameters	Phone screen or clinical evaluation
4. Raynaud syndrome (Raynaud phenomenon)	Phone screen or clinical evaluation

Protocol Summary Form

5. Involvement in any therapeutic trials listed on clinicaltrials.gov, including exercise	Phone screen or clinical evaluation
6. Clinical use of steroid therapy, which would impact the HPA-axis and other physiological systems (e.g., oral dexamethasone, prednisone, or similar)	Patient clinical records Phone screen or clinical evaluation

Study Procedures

We will only recruit and see one participant per week, as per the standard MiSBIE protocol. This low scheduling frequency eliminates any possible exposure between participants.

The study will unfold in two visits, distributed over two consecutive days. For review purposes, the study “Data Collection Form” (Appendix #5) in addition to a Study diagram summarizing study procedures in chronological order (Figure 1), are uploaded with this protocol. Breaks have been built into the study protocol, and participants are free to request breaks at any time. The study procedures comprise eight parts:

Participants who have family member with 3243A>G mitochondrial DNA mutation or deletion and/or who suspect they have the mutation or deletion will be asked to confirm through genetic testing prior to participation. [name] will approach these patients with information regarding genetic testing. These participants will provide a buccal cell or urine sample to test for mitochondrial variants. This genetic testing procedures (consent, sample obtain, genetic consult) will occur online over video chat or at the research site. The

Protocol Summary Form

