- (1) Recruitment: Patients with mitochondrial disease and healthy age/sex/race/physical activity level-matched controls will be recruited. As part of existing clinical care, some patients will have undergone (a) neuropsychological assessment, (b) metabolic assessment and (c) structural magnetic resonance imaging (MRI) as part of the diagnostic services of the Clinical Research Center for Muscular Dystrophy and Related Diseases Laboratory. From this patient pool, those molecularly identified to carry mtDNA defects (m.3243A>G, single deletion) will be provided with a study brochure and invited to sign a form agreeing to be contacted for future research. Potential participants will be contacted directly by the clinical coordinator or study coordinator who will provide information concerning the MiSBIE study and assess inclusion/exclusion criteria over the phone or in person. Should potential participants be interested in the study, they will be forwarded consent forms for their review.

We will screen participants for COVID symptoms at the following timepoints: during the initial screening call: the Monday night before the participant arrives, the Tuesday morning of study activities and the Wednesday morning of study activities. We will take the participant's temperature before starting study activities. We have a no-touch thermometer used for other MiSBIE procedures and have the required expertise to perform this measure.

Protocol Summary Form

[figure not shown]

Figure 1. Diagram illustrating study design and workflow.

Protocol Summary Form

For participants who agree to participate in the study, the a 2-day visit at the Columbia University Irving Medical Center will be scheduled and transportation/lodging arranged. Outside participants will be housed at the Edge Hotel (Washington Heights, [name]), and given detailed instructions to follow prior to their arrival.

(2) Initial Blood Draw and Biological Samples Collection: On the first outpatient visit (Day 1), a fasting blood draw to index allostatic load and cell isolation for mitochondrial function measurements and DNA/RNA analyses. Participants will first arrive at the Division of Behavioral Medicine, Presbyterian Hospital, 15th floor at 9:00am and will be greeted by [name], the MiSBIE study coordinator. Participants will have been instructed not to eat or drink beverages other than water starting at midnight the previous day.

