Mitochondrial Stress, Brain Imaging, and Epigenetics (MiSBIE)

Statistical Analysis Plan

NCT04831424

October 6, 2023

Outcome Measures

Primary Outcome Measure:

1. *Average TSST-induced elevation in cortisol*

This is designed to measure cortisol reactivity to the trier social stress test (TSST), quantified from salivary cortisol (LC-MS) over an 8-timepoints timecourse. The elevation will be measured as the area under the curve (AUC) for the cortisol time course.

[Time Frame: Day 1 post challenge (approximately 2 hours)]

SAP and Results: The AUC analysis for salivary cortisol reactivity to the TSST utilized two metrics: AUCg, where the ground is set at zero, and AUCi, where the ground is set at the baseline level. Given the non-Gaussian distribution of both groups, we applied the Mann-Whitney U test to compare the Control and MitoD groups. For AUCg, the MitoD group's cortisol level was 31.9% higher than the Control (64.49 ng/mL vs. 48.97 ng/mL), but this difference was not statistically significant ($p = 0.40$). The AUCi showed a significant 86.8% higher level in the MitoD group compared to the Control (20.91 ng/mL vs. 11.21 ng/mL, $p = 0.049$).

2. *Average allostatic load index*

Groups will be compared on a quantitative allostatic load (AL) index integrating baseline fasting measures of neuroendocrine, immune and metabolic systems, urinary catecholamines, hematological measures, and hair/diurnal cortisol levels.

[Time Frame: Blood collected on Day 1]

SAP and Results: We calculated allostatic load using the standard count-based index (Juster et al., 2024). In short, for each biomarker, we calculated the 12.5th, 25th, 75th, and 87.5th percentile according to sex-specific reference ranges. We used these percentiles to score each variable as either dysregulated (1) or not dysregulated (0) and summed each variable's score to produce the final allostatic load value. Using the non-parametric Mann-Whitney test, we find that allostatic load is significantly higher in participants with mitochondrial disease than in controls ($p = 0.018$), with a medium effect size (Hedge's $g = 0.52$).

Secondary Outcome Measures:

3. *Average TSST-induced elevation in heart rate*

Groups will be compared on heart rate (HR) as a measure of cardiovascular reactivity to stress, monitored using a continuous 3-lead ECG. The elevation will be computed from the baseline HR to the peak HR reached during the TSST.

[Time Frame: Day 1 post challenge (approximately 2 hours)]

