SAP and Results: Given the non-Gaussian distribution of this data, we conducted the Kruskal-Wallis test to examine differences in heart rate elevation among four clinical groups.

Given the non-Gaussian distribution of this data, we conducted a Mann-Whitney U test to examine differences in heart rate elevation between the control group and combined mitochondrial disease groups (m.3243A>G, MELAS, and deletion). The Mann-Whitney U test indicated that there were no statistically significant differences in heart rate elevation among the groups ($p = 0.42$, $d = 0.27$).

4. ***Correlation between anxiety and mitochondrial respiration***

The association between mitochondrial respiration using extracellular flux analysis (Seahorse) on blood lymphocytes, and anxiety symptoms measured using the state and trait anxiety inventory (STAI), will be quantified by a linear regression across all study participants.

[Time Frame: Day 1]

SAP and Results: Mitochondrial respiration in isolated lymphocytes was measured on a XFe96 Seahorse extracellular flux analyzer. In brief, 0.25M live lymphocytes were seeded in an extracellular flux cell culture plate, and a MitoStressTest was performed following the manufacturer's protocol. Baseline oxygen consumption rate (OCR) was corrected for non-mitochondrial respiration (OCR after rotenone/antimycinA injection) to quantify basal mitochondrial respiration. Linear regression analysis across all participants revealed that higher values of mitochondrial respiration in isolated lymphocytes are associated with lower *state* anxiety ($R^2 = 0.05$, $p = 0.04$). However, the relationship between mitochondrial respiration and *trait* anxiety was not significant ($R^2 = 0.01$, $p = 0.49$).

5. ***Average neuropsychological function***

Groups will be compared on the fluency/initiation domain of executive functioning assessed using the Delis-Kaplan Executive Function System (D-KEFS) test.

[Time Frame: Day 2 neuropsychological session]

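### The Protocol gives two control-matching rules that disagree on target and factors, one of them leaving out the MELAS group, while the SAP compares these controls with pooled patients that include MELAS and mostly does not adjust

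*Protocol*

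**What the plan says.** **Matching rule in the sample description.** Protocol, Description of Subject Population, Sample #3 (Controls): "These participants will be age-, sex- and physical activity level- matched to participants from Groups 1 and 2". MELAS patients are a separate sample (Sample #4, Group 4), and no section names them as a matching target. Their inclusion criterion reads "Carries the m.3243A>G point mutation and has had at least one stroke-like episode, seizure, or both", whereas Groups 1 and 2 exclude strokes and seizures.

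**Matching rule in the procedures.** Protocol, Study Procedures, Day 1, item (1) Recruitment: "Patients with mitochondrial disease and healthy age/sex/race/physical activity level-matched controls will be recruited". This adds race and does not limit the patients to particular groups.

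**The comparisons.** For heart rate (SAP, secondary outcome 3) the test is "between the control group and combined mitochondrial disease groups (m.3243A>G, MELAS, and deletion"; secondary outcome 5 (D-KEFS) names the same three groups. For the primary outcomes, cortisol compares Control with a group labelled MitoD, and allostatic load compares controls with participants who have mitochondrial disease. Neither lists its groups. All four are unpaired Mann-Whitney tests. A Kruskal-Wallis test across four groups is mentioned for heart rate, without a result.

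**Handling of the matching factors.** Allostatic load biomarkers are scored "according to sex-specific reference ranges", and D-KEFS scores are age-adjusted from the control group. The SAP gives nothing further on this, and no group sizes.

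**The concern.** Patients and controls are not randomised, so matching at recruitment is the main protection against differences in age, sex and activity. An unpaired rank test adds none. Controls chosen to resemble Groups 1 and 2 are built for 60 of the 90 planned patients and then compared with a pool that includes the other 30. Group 4 is defined by events that the other two groups exclude, so its age, sex and activity mix cannot be assumed to be the same.

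The factor lists matter too. Staff working from the sample description have no instruction on race, and staff working from the Recruitment section do.

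The primary outcomes are the most exposed. Neither is adjusted for age or activity, although the SAP treats age as relevant enough to adjust D-KEFS for it.

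**Working it through.** **1. Planned numbers reproduced.** Each patient group: 30 × 1.10 = 33, as stated ("33 (accounting for 10% attrition or unusable data"). Controls: 100 + 10 + 8 = 118, as stated ("118 (accounting for 10% attrition or unusable data n=10 and pilot testing n=8").

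**2. Planned MELAS share.** Completers: 30 / (30 + 30 + 30) = 33.3%. Enrolled: 33 / 99 = 33.3%. Controls per patient: 100/60 = 1.67 against Groups 1 and 2, and 100/90 = 1.11 against all three patient groups.

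**3. The two matching rules side by side.**

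| | Sample #3 | Recruitment |
|---|---|---|
| Target | Groups 1 and 2 | mitochondrial disease patients, no group limit |
| Factors | age, sex, activity | age, sex, race, activity |

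**4. What the SAP accounts for, by outcome.**

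| Outcome | MELAS in the patient group | Age | Sex | Activity | Race |
|---|---|---|---|---|---|
| Cortisol AUC (primary) | probable, label undefined | no | no | no | no |
| Allostatic load (primary) | probable, label undefined | no | sex-specific ranges | no | no |
| Heart rate | explicit | no | no | no | no |
| D-KEFS | explicit | yes | no | no | no |

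**5. Size under assumed values.** Suppose controls match Groups 1 and 2 exactly, Group 4 differs by D (in SD of age), and age correlates r with the outcome. Then the pooled age shift is share × D, and the shift in the standardised contrast is share × D × r. The documents give neither D nor r; I assume D = 0.5 to 1.0 and r = 0.3 to 0.5.

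- Low end: (30/90) × 0.5 × 0.3 = 0.05.
- High end: (30/90) × 1.0 × 0.5 = 0.17.

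The sign is that of D × r. With r positive, an older Group 4 would inflate a patient excess and a younger one would hide part of it.

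**6. Is one-third the share actually analysed?** This cannot be confirmed. Two reported results suggest far fewer than the planned 190 completers (100 + 90):

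- Anxiety regression, R² = 0.05 and p = 0.04: t = √[R²(N − 2)/(1 − R²)] gives N of about 85 (74 to 100 allowing for rounding). At N = 190, p would be about 0.002.
- Allostatic load, g = 0.52 and p = 0.018 (z = 2.37): n₁n₂/N = (2.37/0.52)² ≈ 20.7. At the planned 10:9 split, N = 20.7 × 1.9²/0.9 ≈ 83. This is a normal approximation.

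The result in step 5 scales with the share. With 10 MELAS patients among 70 (14%), for example, it becomes 0.14 × 0.5 × 0.3 = 0.02 to 0.14 × 1.0 × 0.5 = 0.07.

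**7. Against the reported allostatic load result.** On the same approximation, p reaches 0.05 at g = 0.52 × 1.96/2.37 = 0.43, a margin of 0.09. Removing 0.05 leaves g = 0.47, z = 2.14 and p of about 0.03. Removing 0.17 leaves g = 0.35, z = 1.59 and p of about 0.11. A shift in the other direction would strengthen the result. Cortisol AUCi, at p = 0.049, has almost no margin.

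**The case against.** The best defence is that the Recruitment section sets no group limit, so its matching can be read as covering MELAS patients. The Protocol also calls Group 4 the same diagnostic group as Group 1. This stands as a possible reading, and it rules out saying flatly that Group 4 is unmatched. It does not remove the problem, because the section that states the target explicitly names two groups.

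The factor lists are nested: controls matched on all four factors also satisfy the shorter list. That is fair. The shorter list is incomplete rather than incompatible, but someone following it alone would not match on race.

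There is some analytical protection. D-KEFS is age-adjusted, allostatic load uses sex-specific ranges, and the Protocol's Background section plans symptom covariates. Those covariates are not the matching factors, and no group comparison in the SAP uses them.

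Three stronger readings are tempting and not supported:

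- **That the analysed patient group is one-third MELAS.** That is the planned share; the SAP reports no group sizes.
- **That MELAS patients alone could carry a bias close to the whole reported effect.** The assumptions in step 5 give 0.15 to 0.5 SD for a MELAS-only contrast (0.5 × 0.3 to 1.0 × 0.5). The reported g of 0.52 is for the single patient group, and the SAP reports no MELAS-only result, so the two must not be set side by side.
- **That the primary results are inflated.** No age, sex or activity data by group are given, all groups share the 18 to 60 range, and the bias could run either way.

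**Conclusion.** The point holds as a mismatch between a stated matching rule and the comparisons made. The Protocol contradicts itself on target and factors, and the rule with an explicit target omits a group that the SAP pools with the others. Pooling is explicit for two secondary outcomes and a probable reading for the two primaries. Most comparisons make no allowance for the matching factors.

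What is shown is exposure to confounding, not a demonstrated bias. The shift of 0.05 to 0.17 SD in either direction rests on assumed values of D and r, exact matching to Groups 1 and 2, and the planned one-third share. It is modest, yet part of that range exceeds the 0.09 margin of the allostatic load result. The correction is cheap and worth making.

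**What to change.** **Protocol.** Give one matching target (Groups 1, 2 and 4) and one factor list, stating whether race is included, in both Sample #3 and the Recruitment section. Apply it to any control slots still open. The SAP already reports results and nothing shows that slots remain, so the analysis changes matter more.

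**SAP.**

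- Define MitoD by listing its groups, and use that definition for every outcome.
- Report the number analysed and the distribution of each matching factor by group.
- Adjust or weight the control-versus-patient comparisons for age, sex and physical activity, and for race if it is kept.
- Add a sensitivity analysis that excludes Group 4.

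Since results are already known, label the added analyses as specified after the fact.

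**Cost.** Wording changes in two Protocol sections, a little more analysis, and some loss of effective sample size if weighting is used. No extra participants are needed.

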Mitochondrial Stress, Brain Imaging, and Epigenetics (MiSBIE)

NCT04831424
October 6, 2023

Lay Summary of Proposed Research

Age-related physical and cognitive decline, as well as the risk of neurological diseases, are increased by the effects of psychosocial stress. Psychosocial stress triggers neuroendocrine, metabolic, cardiovascular, and inflammatory changes in the body. These changes vary in nature and magnitude between individuals, and are associated with long-term disease risk. However, the biological determinants of the stress response are not well understood. Why do some individuals respond more strongly than others to the same stressor?

Our preclinical studies in mouse models with dysfunctional mitochondria, a cellular organelle which produces energy and signals of adaptation, indicate that mitochondria regulate how different organ systems and major stress response axes are activated during psychological stress. This project aims to translate this discovery in a population of individuals with varying degree of mitochondrial dysfunction, and to test potential neural mechanisms. This study will take place at Columbia University Irving Medical Center (CUIMC) and the Mortimer B. Zuckerman Mind Brain Behavior Institute (ZMBBI) and will recruit patients with genetic mitochondrial disease and healthy controls.

Each participant will be studied over two days. On Day 1, we propose to monitor dynamic changes in different hormones and molecules in blood (catecholamines, inflammatory cytokine interleukin 6) and saliva (cortisol) in response to a standardized laboratory "stressor". Participants will also undergo a medical assessment. On Day 2, we propose to examine whether these changes are mediated by inter-individual differences in functional connectivity among different brain regions measured by functional magnetic resonance imaging (fMRI).

Participants will also complete a questionnaire package to evaluate psychosocial functioning and clinical disease severity as well as undergoing a neuropsychological assessment. This interdisciplinary project leverages access to a unique population of patients with genetically

Protocol Summary Form

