To translate our preclinical findings and test these hypotheses with the same level of genetic specificity in humans, we leverage our access to a population of patients with molecularly defined m.3243A>G mtDNA mutation and individuals with single large scale mtDNA deletions in our clinical service for mitochondrial disease at CUIMC. To ascertain if the observed associations are linked to symptom types, we will also recruit individuals with the m.3243A>G mutation who have experienced stroke-like episodes or seizures. These symptoms characterize a clinical subtype known as MELAS (mitochondrial encephalopathy, lactic acidosis, and stroke-like episodes).

Aim 1: Determine the effect mtDNA m.3243A>G and single mtDNA deletion on chronic and reactive stress biomarkers.

Longitudinal studies of stress biomarkers demonstrate that cumulative dysregulation of the HPA (hypothalamic-pituitary-adrenal) and SAM (sympathetic- adrenal- medullary) axes, cardiovascular, metabolic, and pro-inflammatory systems predispose to chronic physical and cognitive decline that overlap with symptoms of mitochondrial diseases. *We hypothesize that patients with mtDNA defects (m.3243A>G) will manifest elevated allostatic load and stress reactivity compared to healthy controls.* This will be assessed on a first hospital visit (Day 1) with repeated measures of blood (catecholamines, inflammatory cytokine IL-6), saliva (cortisol), and cardiovascular monitoring (heart rate variability, blood pressure) in response to a validated laboratory stress protocol, the socially evaluated cold pressor test (SECPT), which elicits strong multi-systemic reactivity. Results from this aim will establish for the first time the effect of inherited mtDNA defects on the nature and magnitude of stress responses in humans, and evaluate their association with patients' symptoms.

Aim 2: Assess DNA methylation signatures and cell aging in patients with the m.3243A>G mutation and single mtDNA deletion.

Mitochondrial signaling involves the production of diffusible signals that alter the epigenetic machinery and the expression of most genes in the human genome; and stress alters DNA methylation in brain remodelling and stress reactivity genes. *We hypothesize that patients with mitochondrial disease will show abnormal baseline DNA methylation signatures, and*

Protocol Summary Form

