4. Strokes & seizures.	Patient clinical records, and self-report
5. Raynaud's syndrome (Raynaud phenomenon)	Phone screen or clinical evaluation
6. Involvement in any therapeutic trials listed on clinicaltrials.gov, including exercise	Phone screen or clinical evaluation
7. Clinical use of steroid therapy, which would impact the HPA-axis and other physiological systems (e.g., oral dexamethasone, prednisone, or similar)	Patient clinical records Phone screen or clinical evaluation

Group 3 (Controls)

CRITERION	METHOD OF ASCERTAINMENT
Inclusion:	
1. Individuals between the age of 18- 60.	Patient clinical records Phone screen or clinical evaluation
2. Willing to provide saliva samples and have venous catheter installed for blood collection during the hospital visit	Phone screen or clinical evaluation
3. Willing to provide informed consent and capacity to consent	Self report
4. Use of effective method of birth control for women of childbearing capacity	Phone screen or clinical evaluation

Protocol Summary Form

5. English Speaking	Self report, Phone screen or clinical evaluation
Exclusion:	
1. Individuals with cognitive deficit incapable of providing informed consent will not be included	TICS scores ≥ 30 , administered via phone screen or clinical evaluation
2. Symptoms of flu or other seasonal infection four weeks preceding hospitalvisit, as this would influence immune system parameters	Phone screen or clinical evaluation
3. Raynaud's syndrome (Rayneau phenomenon)	Phone screen or clinical evaluation
4. Involvement in any therapeutic trials listed on clinicaltrials.gov, including exercise	Phone screen or clinical evaluation
5. Metal inside or outside the body or claustrophobia prohibitive to MRI testing	Phone screen or clinical evaluation
6. Diagnosed with mitochondrial disease m.3243A>G, or large scale mtDNA deletion	Phone screen or clinical evaluation

Group 4 (m.3243A>G with MELAS symptoms

CRITERION	METHOD OF ASCERTAINMENT
Inclusion:	
1. Patients between the age of 18- 60.	Patient clinical records Phone screen or clinical evaluation

Protocol Summary Form

2. Willing to provide saliva samples and have venous catheter installed for blood collection during the outpatient visit	Phone screen or clinical evaluation
3. Willing to provide informed consent and capacity to consent	Self-report and clinician assessment
4. Use of effective method of birth control for women of childbearing capacity	Phone screen or clinical evaluation

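### Steroid therapy is an exclusion in every patient group but not in controls, so the rules permit a one-sided confounder of the cortisol outcomes; the effect is probably small but should be checked and reported

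*Protocol*

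**What the plan says.** In the protocol's Inclusion/Exclusion Criteria, exclusion 7 for Groups 1 and 2 and exclusion 6 for Group 4 both remove participants for "Clinical use of steroid therapy, which would impact the HPA-axis and other physiological systems (e.g., oral dexamethasone, prednisone, or similar".

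The Group 3 (control) list has six exclusions: cognitive deficit, recent infection, Raynaud's, another therapeutic trial, "Metal inside or outside the body or claustrophobia prohibitive to MRI testing", and "Diagnosed with mitochondrial disease m.3243A>G, or large scale mtDNA deletion". None concerns steroids or any other medication.

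Controls are described as healthy in several places. The Lay Summary says the study "will recruit patients with genetic mitochondrial disease and healthy controls". Sample #3 says "We will study healthy individuals without a diagnosis of mitochondrial disease recruited from the community". The Recruitment paragraph says "Patients with mitochondrial disease and healthy age/sex/race/physical activity level-matched controls will be recruited". None of these gives the word a medication rule, and medication is not a matching factor.

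The SAP's Primary Outcome 1 is salivary cortisol AUC. Primary Outcome 2 is an allostatic load index whose components include hair and diurnal cortisol. Both are compared by Mann-Whitney tests without covariates. The reported results are AUCi p = 0.049, AUCg p = 0.40 and allostatic load p = 0.018.

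**The concern.** The protocol gives its own reason for the patient exclusion: steroid therapy disturbs the HPA axis. That reason applies equally to a control whose cortisol is being measured. A rule applied to one side of a comparison only can let the exposure differ between groups by design.

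The Aim 1 hypothesis is that patients "will manifest elevated allostatic load and stress reactivity compared to healthy controls". If steroids lowered salivary cortisol in some controls, the bias would tend to favour that hypothesis. Lowering is an assumption here, because the documents say only that the axis is affected. For the allostatic load index the direction is unknown. Of the two cortisol metrics only AUCi crosses 0.05, so that is the cortisol conclusion a few affected controls could alter.

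**Working it through.** **1. Could anything else in the plan correct an imbalance?** Matching covers age, sex and physical activity (Sample #3), with race added under Recruitment. The covariates named in the Background are depressive, burnout and other symptoms. The SAP tests use none. Nothing visible addresses medication.

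**2. The SAP's own figures.** The p-value cannot be rebuilt, because analysed numbers and ranks are not given. The stated values give 20.91/11.21 = 1.865, or +86.5% (stated 86.8%), and 64.49/48.97 = 1.317, or +31.7% (stated 31.9%). These small mismatches do not affect the point. Two-sided p = 0.049 corresponds to z = 1.969, against a limit of 1.960.

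**3. What sample size to assume.** Planned completers are 100 controls and 3 × 30 = 90 patients. The SAP's results suggest fewer were analysed.
- Allostatic load has g = 0.52 with p = 0.018. Approximating t = g × √(n1·n2/(n1+n2)), 100 v 90 gives t = 3.58 and p of about 0.0004. By contrast 45 v 38 gives t = 2.36, and 70 v 29 gives t = 2.36, each with p of about 0.02.
- The anxiety regression has R² = 0.05 with p = 0.04. With t = √(R²(n−2)/(1−R²)), n = 85 gives t = 2.09 and p = 0.040. Rounding of both figures allows about 74 to 100.

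These are inferences, and numbers may differ by outcome, so a range is used.

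**4. Removing controls.** With n1 controls and n2 patients (normal approximation, no ties):
- SD(U) = √(n1·n2·(n1+n2+1)/12); excess E = z0 × SD(U).
- Removing k controls who each rank below a share f of patients gives E′ = E − k(f − 0.5)n2, tested against SD(U) with n1 − k controls.

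Example, AUCi at 70 v 29: SD = √(70·29·100/12) = 130.06 and E = 1.969 × 130.06 = 256.0. Removing one control below all patients gives E′ = 256.0 − 14.5 = 241.5, SD = √(69·29·99/12) = 128.48, z = 1.880, p = 0.060.

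| Controls v patients (assumed) | AUCi, one removed: below all patients | at patients' median | above all patients | AUCg, three removed, all below | Allostatic load, three removed, all below |
|---|---|---|---|---|---|
| 45 v 38 | 0.068 | 0.045 | 0.029 | 0.74 | 0.052 |
| 60 v 25 | 0.061 | 0.046 | 0.034 | 0.62 | 0.036 |
| 70 v 29 | 0.060 | 0.046 | 0.035 | 0.60 | 0.035 |
| 70 v 40 | 0.062 | 0.046 | 0.034 | 0.63 | 0.039 |
| 100 v 90 | 0.062 | 0.047 | 0.035 | 0.62 | 0.040 |

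Removing three controls who rank above all patients takes AUCg to 0.15–0.22 at these sizes, still above 0.05.

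**5. Type I error, worst case.** Suppose there is no true difference and a share c of controls ranks below every patient. Then z shifts by (c/2)·n1·n2/SD(U). At 70 v 29 with c = 5%, the shift is 0.025 × 2030/130.06 = 0.39, and the two-sided error is 6.8%. Over the sizes in the table it is 5.1–5.2% for c = 1%, 5.2–5.7% for c = 2% and 6.5–9.1% for c = 5%.

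**The case against.** The strongest reply is that no defect in the data has been shown. The excluded exposure is treatment for a clinical condition, and controls are described as healthy, so few if any would have had it. Eligibility is ascertained by phone screen or clinical evaluation in all groups. The Data Collection Form (Appendix 5), the compliance forms (Appendices 8 and 9) and the screening database are not in the available text and may have captured medication. The lists differ in other items too: MRI contraindications appear for controls only and neoplastic disease for patients only, so this may be a drafting gap.

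The second reply is that the AUCi sensitivity is mostly the nearness of 0.049 to 0.05, which leaves it open to almost any small exclusion. Nor need a steroid-using control rank last. AUCi is measured from baseline, so a flat, suppressed curve gives a value near zero, and other participants can be negative. Removing a high-ranking control would strengthen the result.

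All of this stands, and it limits the size of the point. It does not remove the gap. The description of controls as healthy carries no medication rule. The control list spells out recent infection with its immunological reason but does not carry over the parallel HPA criterion.

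A reader might go further and infer that steroid-using controls were enrolled and produced the AUCi difference. The documents do not support that: they report no medication use in any group.

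**Conclusion.** The asymmetry is certain from the text; its consequence is not. The rules permit a one-sided exposure to a confounder that the protocol names, and the unadjusted tests would not correct it. The expected effect is probably small. That rests on healthy controls rarely taking steroids, which the documents neither confirm nor exclude.

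If low-ranking controls were affected, a single one would be enough to move AUCi from 0.049 to about 0.060–0.068 over the assumed sizes. One at the patients' median would not move it past 0.05. The AUCg conclusion does not change under the removals tried. Allostatic load generally stays below 0.05 with three worst-case removals but reaches 0.052 at 45 v 38, so its robustness depends on the analysed number.

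It would be wrong to read this as showing that the AUCi result is invalid or biased in a known direction. What the documents support is a request for a check and a short report.

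**What to change.** - Reconcile the steroid criterion between the patient and control lists for any further enrolment, or state why they differ.
- Search existing screening, clinical-history and data-collection records, and report the number of steroid users by group. If use was not recorded, say so and list it as a limitation of the AUCi result.
- If any controls used steroids, report AUCg, AUCi and allostatic load with and without them as a labelled post-hoc sensitivity analysis. Keep the original analysis as primary, because the results are already known.
- State the analysed number per group for each outcome.

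The cost is one line in the eligibility table, one records check and, if there are users, one re-run. No participant leaves the primary analysis. If no control used steroids, one sentence saying so closes the point.
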